7.8 Withdrawal criteria

It will be clearly stated that the participant is free to withdraw from the study at any time for any

reason without prejudice to future care, and with no obligation to give the reason for withdrawal.

If the data has already been anonymised, this cannot be removed. However there will be no further data capture following withdrawal of consent.

7.10 Assessment and management of risk

The monitoring equipment to be used, are CE marked and are being used in its licensed indication. This research does not involve the testing of the monitoring equipment. The safety and suitability of the monitoring equipment will be confirmed prior to study being conducted by the Medical Physics team.

Infection control procedures for the equipment will be conducted in line with organisational (University and NHS) policies and procedures due to the COVID pandemic.

We will be using a University of Leicester tablet linked to a University of Leicester email address to collect data from the sensors. Only the participant ID number will be stored when the sensors are being used. Once the data has been transferred onto the University's server, the data from the tablet will be deleted.

Interviews will be recorded on an encrypted USB voice recorder. The surgeon's ID number will be mentioned at the beginning of the recording to maintain anonymity. The voice recorder will be stored securely at the University of Leicester, in secure cupboard in a locked room. Once the recordings have been transferred to the servers, they will be deleted from voice recorder. Voice recordings will be transcribed by the research team or by a transcribing company. If a transcribing company is used, a confidentiality agreement will be executed. Any quotes used in publications will be anonymised and the participant will not be identified from them.

7.11 End of trial

As soon as data has been collected and analysed.

8. Storage and analysis of samples

Samples will be stored at the RKCSB. The saliva samples will then be sent to a commercial organisation for analysis and an agreement will be in place for the services that is provided. Samples will then be destroyed in line with the HTA's guidance. At the validation stage this is no longer applicable as no salivary cortisol swabs will be taken / stored following this amendment. The previously obtained salivary samples (ie prior to the amendment) will be sent to a commercial organisation for analyse and agreement will be in place for the services that is provided. Samples will then be destroyed in line with the HTA's guidance

9. Recording and reporting of SAEs

9.1 Definitions

Term	Definition

Adverse Event (AE)

Any untoward medical occurrence in a patient or clinical investigation participants, which does not necessarily have to have a causal relationship with this treatment.

An AE can therefore be any unfavourable and unintended sign (including an abnormal laboratory finding), symptom or disease temporally associated with the the study, whether or not considered related to the study.

Adverse Reaction (AR)	An untoward and unintended response in a participant to an investigational medicinal product which is related to any dose administered to that participant.				
	The phrase "response to an investigational medicinal product" means that a causal relationship between a trial medication and an AE is at least a reasonable possibility, i.e. the relationship cannot be ruled out.				
	All cases judged by either the reporting medically qualified professional or the Sponsor as having a reasonable suspected causal relationship to the trial medication qualify as adverse reactions. It is important to note that this is entirely separate to the known side effects listed in the SmPC. It is specifically a temporal relationship between taking the drug, the half-life, and the time of the event or any valid alternative aetiology that would explain the event.				
Serious Adverse Event (SAE)	A serious adverse event is any untoward medical occurrence that:				
	 results in death is life-threatening requires inpatient hospitalisation or prolongation of existing hospitalisation results in persistent or significant disability/incapacity consists of a congenital anomaly or birth defect 				
	Other 'important medical events' may also be considered serious if they jeopardise the participant or require an intervention to prevent one of the above consequences.				
	NOTE: The term "life-threatening" in the definition of "serious" refers to an event in which the participant was at risk of death at the time of the event; it does not refer to an event which hypothetically might have caused death if it were more severe.				
Serious Adverse Reaction (SAR)	An adverse event that is both serious and, in the opinion of the reporting Investigator, believed with reasonable probability to be due to one of the trial treatments, based on the information provided.				
Expected Serious Adverse Events/Reactions	There are none expected for this type of research study but if any are identified, these will be reported in line with Sponsor's SOPs.				
Suspected Unexpected Serious Adverse Reaction	A serious adverse reaction, the nature and severity of which is not consistent with the information about the medicinal product in question set out in the reference safety information:				
(SUSAR)	 in the case of a product with a marketing authorisation, this could be in the summary of product characteristics (SmPC) for that product, so long as it is being used within it's licence. If it is being used off label an assessment of the SmPCs suitability will need to be undertaken. in the case of any other investigational medicinal product, in the investigator's brochure (IB) relating to the trial in question 				

9.2 Reporting procedures for All Adverse Events

There are none expected for this type of study but if any are expected to be reported, sponsor processes will be followed.

All AEs occurring during the study observed by the investigator or reported by the participant, whether or not attributed to study, will be recorded on the CRF.

The following information will be recorded: description, date of onset and end date, severity, assessment of relatedness to study, other suspect device and action taken. Follow-up information should be provided as necessary.

AEs considered related to the study as judged by a medically qualified investigator or the sponsor will be followed until resolution or the event is considered stable. All related AEs that result in a participant's withdrawal from the study or are present at the end of the study, should be followed up until a satisfactory resolution occurs.

It will be left to the investigator's clinical judgment whether or not an AE is of sufficient severity to require the participant's removal from treatment. A participant may also voluntarily withdraw from treatment due to what he or she perceives as an intolerable AE. If either of these occurs, the participant must undergo an end of study assessment and be given appropriate care under medical supervision until symptoms cease or the condition becomes stable.

The severity of events will be assessed on the following scale: 1 = mild, 2 = moderate, 3 = severe.

The relationship of AEs to the study will be assessed by a medically qualified investigator.

10 STATISTICS AND DATA ANALYSIS

10.1 Sample size calculation

A key unknown for the feasibility of the full trial is whether it is possible to capture all 5 components of the tool for objective assessing stress of surgery therefore the proportion of surgeries with all 5 variables completely captured will be our primary feasibility outcome.

We believe this will be high, at around at least 90%. A sample size of 65 produces a two-sided 95% confidence interval with a width equal to 0.16 when the sample proportion is 0.90, with lower limit 0.80 and upper limit 0.96. This data will be used to determine the parameters to classify cases into low, intermediate and high impact depending on the physical/psychological impact on the surgeon.

A further 100 cases have been included as validation of the tool. This is based on a 50% prevalence of 'high' impact procedure and 95% confidence level and a sensitivity of 0.90 (0.772-0.970).

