3. RESEARCH QUESTION /OBJECTIVES AND OUTCOME MEASURES/ENDPOINTS

Hypothesis: The physical/psychological impact on surgeons is less with RA compared to SS and open surgery.

Aim: To develop and validate a 5-point assessment tool to objectively measure both the physical and psychological impact of complex surgical cases on a surgeon

in order to give a single categorisation of impact: high, intermediate or low.

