3.1 Primary objective

The proportion of surgical procedures where all 4 variables of the assessment tool are captured (continuous HR monitoring; continuous movement sensor monitoring; STAI questionnaire; WMS questionnaire).

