3.3 Outcome measures/endpoints

To design and validate a 4-point assessment tool that can objectively measure the physical and psychological impact of complex surgical cases on a surgeon. The tool will then be taken forward and used in a large, multi-centre trial to determine whether a difference in surgeon impact exists between the different surgical modalities (open/laparoscopic/robotic) and if so to quantify the magnitude of the difference.

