3.4 Primary endpoint/outcome

The proportion of cases where all the four components of the tool can be collected per case is the primary outcome.

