4. TRIAL DESIGN

This is an observational study with the aim of investigating the impact that open and minimally invasive surgery (including robotic assist and straight stick laparoscopy) can have on surgeons' physical and psychological health.

The study will be using a monitoring tracking equipment called XSENS DOT Sensors, Actiheart heart rate monitor which are CE marked and will be used in its licensed indication. All equipment being used within the UHL operating theatres for the purpose of the study will have approval/authorisation from the medical physics department. The data collected will be downloaded on to a tablet using Bluetooth technology. Cortisol measurements were initially obtained at baseline (for each surgeon), preoperatively /intraoperatively (at time of the removal of specimen) and postoperatively as a biomarker to measure the cognitive impact of surgery. However, process evaluation within the feasibility stage has revealed it to be inconvenient and a potential disruption to theatre workflow especially if more than one case is recruited per list. The cortisol measurements obtained thus far will be included in the preliminary analysis but this biomarker will be omitted in the data collected at the validation stage. Surgeons will be expected to complete the STAI and modified Nordic WMS questionnaires as well. The WMS questionnaires have been further modified following the process evaluation carried out throughout the feasibility stage – to now include a numerical pain score to further objectively evaluate the intensity of the work related injuries sustained/ experienced.

XSENS DOT

ACTIHEART HEART RATE MONITOR

The research involves working in collaboration with the wearable robotics team at Loughborough University.

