10.3.2 Primary outcome analysis

Multi-variate analysis will be performed to identify factors increasing surgeon impact and statistical modelling will be used to calculate a single value that is representative of the cumulative 'impact' of the case on the surgeon so that cases can be categorised as 'high', 'intermediate' or 'low' impact. Case complexity (for example BMI, previous surgery) and subjective surgeon opinion will be compared with the impact classification to determine internal consistency (Cronbach alpha) and content validity.

Following the development of the impact classification, geographical external validation will be conducted at additional sites, and surgeons recruited to confirm the accuracy of the 5-point assessment tool.

Data gathered from the interviews will undergo qualitative analysis

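### Section 10.1 sizes the primary feasibility outcome on five captured variables, while sections 3.1 and 3.4 define it on four

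*Protocol*

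**What the plan says.** The current text of the protocol (v5.0) gives the primary outcome in two forms.

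- **Five.** Section 10.1: "the proportion of surgeries with all 5 variables completely captured will be our primary feasibility outcome". The expectation of about 90% and the interval for 65 procedures follow directly from that sentence.
- **Four.** Section 3.1: "The proportion of surgical procedures where all 4 variables of the assessment tool are captured", followed by a list of continuous heart rate, continuous movement sensors, STAI and WMS. Section 3.4: "The proportion of cases where all the four components of the tool can be collected per case is the primary outcome".

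The description of the tool is split in the same way.

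- The Aim in section 3: "To develop and validate a 5-point assessment tool to objectively measure both the physical and psychological impact".
- Section 10.3.2, on external validation: "confirm the accuracy of the 5-point assessment tool".
- Section 3.3: "To design and validate a 4-point assessment tool".

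Section 4 explains that cortisol was measured at first, that process evaluation in the feasibility stage found it inconvenient and potentially disruptive in theatre, and that "this biomarker will be omitted in the data collected at the validation stage". Section 8 confirms that no swabs are taken after the amendment. Samples already collected stay in the preliminary analysis (section 3.2, item 11).

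**The concern.** The primary outcome is a simple proportion, so its definition decides the result. An analyst who follows 10.1 counts a procedure with heart rate, movement, STAI and WMS all complete but no cortisol as a failure. An analyst who follows 3.4 counts it as a success. Both are following the protocol.

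The planning assumption is affected too. Section 10.1 attaches the 90% expectation to the five-variable outcome, and nowhere does the protocol say what capture is expected for the four-component outcome that section 3 names as primary. Nor does it say how feasibility procedures done while cortisol was still collected are to be scored, although they belong to the group of 65 on which the outcome was sized.

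**Working it through.** **1. The plan's own figure.** Inputs from section 10.1: n = 65, expected proportion 0.90, two-sided 95% confidence, stated limits 0.80 and 0.96, stated width 0.16. With x = 0.90 × 65 = 58.5, the exact (Clopper-Pearson) limits are:

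- lower = 2.5% quantile of Beta(x, n − x + 1) = Beta(58.5, 7.5), giving 0.8002
- upper = 97.5% quantile of Beta(x + 1, n − x) = Beta(59.5, 6.5), giving 0.9605
- width about 0.160

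The stated interval reproduces. The number of components does not enter the formula, so changing five to four leaves n = 65 and 0.80 to 0.96 as they are, provided that 90% is still the expected rate.

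**2. Which variable is the fifth.** No section names it. Section 3.1 lists the four that remain, and cortisol is the only measurement that sections 4 and 8 describe as collected and then removed. That it is cortisol is an inference, though a strong one. Steps 3 and 4 rest on it.

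**3. Procedures after the removal.** Without cortisol, five-variable capture is impossible whatever else is recorded. For the validation stage this gives 0 of 100.

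**4. The 65 feasibility procedures.** Let k be the number of the 65 with a cortisol measurement. The highest possible five-variable proportion is k/65. The protocol does not give k, so the range below is assumed:

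| k (assumed) | ceiling k/65 |
|---|---|
| 65 | 100% |
| 50 | 77% |
| 30 | 46% |
| 10 | 15% |

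Since 59/65 = 90.8% and 58/65 = 89.2%, the ceiling is below the expected 90% once k is 58 or fewer. The four-component definition has no such ceiling.

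**5. What a 90% five-variable expectation implies for four components.** A procedure with all five captured also has the four, so the four-component rate is at least 90%. As an illustration only, assume five independent components with equal capture rates, which the protocol does not state. Each rate is then 0.90^(1/5) = 0.979, and the four-component rate is 0.90^(4/5) = 0.919. The exact interval at n = 65 would be 0.82 to 0.97, width 0.148. The sample size would still be enough.

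**The case against.** The strongest reply is that this is incomplete updating after an amendment. The sections that formally set the objective and endpoint, 3.1 and 3.4, agree on four, as do 3.2 (item 1) and 3.3. Only the Aim, 10.1 and 10.3.2 keep five. The sample size is unaffected, and section 10.1 sets no pass mark for the capture rate. Section 4 already gives the reason for dropping cortisol, and section 10.5 already commits to monitoring which component is most often hard to obtain.

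Most of this stands, and it limits the point: the size of the study is not in question and the decision to drop cortisol is not criticised. It does not remove the contradiction, because 10.1 says in terms that five-variable capture is the primary outcome, and nothing in the protocol gives one section precedence.

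A reader might infer three stronger things that the protocol does not support.

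- *That no procedure at all can meet the 10.1 definition.* The interval was planned for the 65 feasibility procedures, and cortisol was collected in that stage. Those with a cortisol measurement can have all five.
- *That cortisol was the component hardest to collect.* Section 4 reports inconvenience and potential disruption. It gives no capture rate for any component.
- *That the four-component rate is favourable by construction.* On the same cases it cannot be lower than the five-variable rate, but the difference is unknown and could be nil. Refining the tool is also a declared purpose of this feasibility study. Multiplying 90% by a guessed cortisol capture rate would not settle the matter, since 10.1 places the 90% on the five-variable outcome, not on the four-component one.

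**Conclusion.** The point holds as a contradiction in the definition of the primary outcome. Taken literally, 10.1 scores every procedure without cortisol as a failure: all 100 validation cases, and any feasibility case done after the removal. For the 65 feasibility cases the difference between the two definitions cannot be calculated, because the number with cortisol and the capture rate of each component are not given. It ranges from none, if cortisol was captured wherever the other four were, to a five-variable ceiling of k/65.

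This rests on cortisol being the fifth variable. If it were something else, the conflict between five and four would remain, but the consequence for procedures without cortisol would not follow. The figures n = 65 and 0.80 to 0.96 are correct and need no change. What needs restating is the outcome to which they, and the 90%, refer.

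**What to change.** 1. In the Aim (section 3), section 10.1 and section 10.3.2, replace the five-component, five-variable and five-point wording with the four components named in 3.1, so that one definition governs the endpoint, the sample size and the validation.
2. In 10.1, state that the 90% expectation and the interval of 0.80 to 0.96 at n = 65 now refer to the four-component outcome.
3. State that all 65 feasibility cases are scored on the four components, and that five-variable capture is also reported for those done while cortisol was in the protocol, with their number.

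The cost is a wording amendment and one extra line in the results table. No new data and no change in sample size are needed.

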Primary	variables of the ass (continuous HR monitoring; S Nordic WMS questionna					
Secondary	of 'impact' (high/interme 2. Validation of the combine vs objective assessmen 3. Analysis of the impact of supervision to surgical monitoring 4. Willingness of recruitmes sample size calculations 5. Identification of primare future definitive multi-ce 6. Optimisation/validation measures to capture events and outcomes 7. Safety assessment of recording devices in the 8. Optimisation of surgicular monitoring during programalysis 9. Optimisation of position movement/activity sensionalysis 10. Optimisation/validation of	f providing surgical training and all trainees using heart rate ent of patients/surgeons and so for a future multi-centre study cy/secondary outcomes for a entre study of patient data recording anaesthetic/operative/clinical of measurement tools and a theatre environment				

FUNDING AND SUPPORT IN KIND

FUNDER(S) (Names and contact details of ALL organisations providing funding and/or support in kind for this trial)	FINANCIAL AND NON FINANCIALSUPPORT GIVEN
Intuitive Surgical Grant	Project grant RM60G0742

ROLE OF TRIAL SPONSOR

The sponsor of this research is the University of Leicester. The University of Leicester is registered as a research sponsor with the Department of Health and routinely takes responsibility as sponsor for research activities within the NHS.

ROLES AND RESPONSIBILITIES OF TRIAL MANAGEMENT COMMITEES/GROUPS & INDIVIDUALS

N/A

ISSUE Protocol Version v5.0 24/09/2022 IRAS: 300580

Simulated Setting

series of standardised exercises to ensure partcipants' technical abilities are not impacted by wearing the equipment

PREOP Assessment

PIL and CIL - should have been distributed preoperatively in either a clinic setting or in pre-eassement setting.

PREOP Day of Surgery

On the day consent forms from both consultant and patient to be obtained.

Preop questionnaire to be completed

PARTICIPANT ID TO BE ALLOCATED

INTRAOP

sensors and heart rate monitor will be kept with a member of the research team (CRF [name])

Surgeons will have their own straps to be used at every procedure that they perform that will be included in the study

Sensors and heart rate monitor will be cleaned inbetween cases and participants in line with the established Infection Control standards within the unit where the study is conducted

POST OP

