3.5 Secondary endpoints/outcomes

- 1. Ergonomic analysis based on BMI including hip, waist ratio
- 2. Global measurements of surgeon including arm span, glove size and height to establish a potential association between ergonomics and anthropometric features of surgeon

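### The stated precision for the primary capture proportion (65 procedures, 0.80 to 0.96) assumes independent procedures, although surgeons contribute repeated procedures

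*Protocol*

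**What the plan says.** The primary outcome is counted per procedure. Section 3.1 defines it as "The proportion of surgical procedures where all 4 variables of the assessment tool are captured" and lists the four: continuous heart rate, continuous movement sensors, the STAI questionnaire and the WMS questionnaire. Section 10.1 gives the precision for a capture proportion of 0.90: "A sample size of 65 produces a two-sided 95% confidence interval with a width equal to 0.16 when the sample proportion is 0.90". The limits stated there are 0.80 and 0.96. (Section 10.1 still counts five components where 3.1 counts four; this does not affect the arithmetic here.)

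Two places show that one surgeon supplies several procedures. The study flow chart, under the intraoperative step, says: "Surgeons will have their own straps to be used at every procedure that they perform that will be included in the study". Section 4, explaining why cortisol sampling was dropped, calls it disruptive "especially if more than one case is recruited per list".

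Section 10.1 mentions no clustering, ICC or design effect. The protocol nowhere gives the number of surgeons or a limit on procedures per surgeon.

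Two related statements matter to a lesser degree. For the second stage, section 10.1 says: "A further 100 cases have been included as validation of the tool", with 50% prevalence of high impact and a sensitivity of 0.90 (0.772 to 0.970). Section 3.5 plans to use arm span, glove size and height to "establish a potential association between ergonomics and anthropometric features of surgeon".

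**The concern.** A binomial interval on 65 procedures treats each procedure as a fresh, unrelated observation. Here the surgeon wears the sensors and the heart rate monitor and fills in both questionnaires. How well the equipment fits, how well it is tolerated and how reliably the forms are completed can all be expected to differ between surgeons. A surgeon with a missing component in one operation is then more likely to have one in the next. In that case 65 procedures carry less information than 65 independent ones, and the sample size section promises more precision than the study can deliver.

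The capture proportion is the study's primary result, and secondary objective 4 uses this study for the sample size of a future multi-centre study. If the precision is overstated, or the correlation between a surgeon's procedures goes unreported, the error carries into that planning.

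**Working it through.** **Inputs from the protocol.** n = 65 procedures, p = 0.90, two-sided 95% (section 10.1).

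**Assumed inputs, not in the protocol.** Number of surgeons k = 5 to 20; ICC = 0.05 to 0.20; equal numbers of procedures per surgeon, m = 65/k.

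**Step 1: reproduce the plan's figure.** With x = 0.90 × 65 = 58.5, the exact (Clopper-Pearson) interval is 0.8002 to 0.9605, width 0.1604. This matches 0.80, 0.96 and 0.16. Other methods do not match all three figures: Wald gives 0.827 to 0.973 (width 0.146), Wilson 0.803 to 0.952 (0.149), and continuity-corrected Wilson 0.794 to 0.957 (0.163). The stated figure therefore contains no allowance for clustering.

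**Step 2: allow for clustering.** Design effect DE = 1 + (m − 1) × ICC; effective n = 65/DE; then the exact interval at 0.90 on the effective n. Example with k = 10: m = 6.5; at ICC 0.10, DE = 1 + 5.5 × 0.10 = 1.55; effective n = 65/1.55 = 41.9; interval 0.768 to 0.971, width 0.20.

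| Surgeons (m) | ICC 0.05 | ICC 0.10 | ICC 0.20 |
|---|---|---|---|
| 20 (3.25) | 0.793–0.963, width 0.17 | 0.786–0.965, 0.18 | 0.773–0.969, 0.20 |
| 13 (5) | 0.788–0.965, 0.18 | 0.776–0.968, 0.19 | 0.754–0.975, 0.22 |
| 10 (6.5) | 0.783–0.966, 0.18 | 0.768–0.971, 0.20 | 0.738–0.978, 0.24 |
| 8 (8.1) | 0.779–0.968, 0.19 | 0.759–0.973, 0.22 | 0.722–0.981, 0.26 |
| 5 (13) | 0.765–0.972, 0.21 | 0.733–0.979, 0.25 | 0.676–0.989, 0.31 |

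Every cell is wider than 0.16. At the top left the difference is about 0.01; at the bottom right the width nearly doubles. Unequal numbers of procedures per surgeon would widen these intervals further.

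**Step 3: does the naive interval under-cover?** Capture was simulated from a beta-binomial model with 65 procedures and a true proportion of 0.90, and the exact interval was computed as if procedures were independent. Coverage under independence is about 98%, because the exact interval is conservative. With clustering:

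- 20 surgeons: about 97% at ICC 0.05, 96% at 0.10 and just under 95% at 0.20.
- 13 surgeons: about 97%, 95% and 92%.
- 8 surgeons: about 95.5%, 92.5% and 86%.
- 5 surgeons: about 79% at ICC 0.20.

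**Step 4: the validation interval.** 50% of 100 gives 50 high-impact cases. At sensitivity 0.90 the exact interval for 50 independent cases is 0.782 to 0.967. The stated 0.772 to 0.970 is slightly wider and corresponds to an exact interval on about 44 cases. It becomes too narrow for 50 cases only when DE exceeds 50/44 = 1.14. With 10 surgeons (5 high-impact cases each) that means ICC above 0.14/4, or about 0.03.

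**The case against.** The strongest reply is that the protocol never says there are few surgeons. Section 5 recruits from both the Gynaecology and Surgical Directorates and expects further sites, and section 10.3.2 adds sites and surgeons for validation. With 20 surgeons or a low ICC, the conservatism of the exact interval absorbs most of the clustering. The outcome is also a descriptive feasibility proportion, and the protocol attaches no progression threshold to its lower limit. All of this stands. It limits the size and severity of the point. It does not restore the independence on which the 0.16 width rests.

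Three stronger readings are tempting, and the document does not support them:

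- *The same few surgeons do all the operations, so the interval is bound to mislead.* No number of surgeons is given, and Step 3 shows coverage at or above about 95% in several plausible cells.
- *The 100-case validation interval has the same fault and is too narrow.* It is not the independent interval for 50 cases. It is a little wider, and falls short only beyond a design effect of about 1.14.
- *The anthropometric associations are pseudo-replicated.* Sections 10.3.2 and 11.3.3 name no model and no unit of analysis, and a statistical analysis plan that is not at hand may include a surgeon effect. A per-procedure regression without one would be pseudo-replicated, but the protocol does not say that this is planned.

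**Conclusion.** The point holds for the 65-procedure precision statement. The arithmetic in section 10.1 is correct for independent procedures; the independence assumption does not fit the design described elsewhere in the protocol. With any positive within-surgeon correlation, the achievable precision is worse than 0.80 to 0.96.

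The size depends on two quantities the protocol does not give. Over the assumed range in Step 2, the loss runs from negligible to serious. Real under-coverage of the naive interval appears when surgeons are few or the ICC is high, and the document does not show whether that will be so. I rate this as moderate: a precision and design assumption to be stated and corrected, not a computational error.

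**What to change.** 1. In section 10.1, state the expected number of surgeons and of procedures per surgeon for each stage.
2. Restate the 65-procedure precision with a design effect over a range of ICCs, labelled as assumptions. The table under Step 2 can serve once the surgeon number is known; no single row should be entered as though it were established.
3. State that the interval for the capture proportion, and the one for validation sensitivity, will be computed with surgeon as the cluster. A beta-binomial model, GEE with a small-sample correction, or a bootstrap that resamples surgeons would each do.
4. Report the number of surgeons, the procedures per surgeon and the estimated ICC, since secondary objective 4 needs them for the future study.
5. Because arm span, glove size and height are constant within a surgeon, state that any analysis of them takes the surgeon as the unit or includes a surgeon effect.

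The cost is a less favourable stated precision and slightly more analysis work. No additional procedures are needed unless the sponsor wants to keep the width at 0.16. At 6.5 procedures per surgeon, scaling 65 by the design effect gives about 83, 101 or 137 procedures at ICC 0.05, 0.10 or 0.20, reached by adding surgeons.
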